### 3. PATIENT SELECTION

#### 3.1. Eligibility criteria:

The eligibility criteria are as follows:

1. Patients must be able to understand and voluntarily sign an informed consent form.
2. Age  $\geq 18$  years at the time of signing the informed consent form.
3. Able to adhere to the study visit schedule and other protocol requirements.
4. Pathologically confirmed disease with A or B as follows:
  - A. AML patients who either have:
    - 1) Relapsed or refractory disease after receiving one or more courses of induction chemotherapy, hypomethylating agent therapy, or bone marrow transplant *or*
    - 2) *de novo* AML but not deemed to be a candidate for conventional therapy based on age, co-morbidities, or patient preference
  - B. MDS, CMML, or MDS/MPN with high risk features as defined below who have relapsed after initial response or are refractory (failure to achieve a CR, PR, or HI) after receiving at least 4 cycles of hypomethylating agents 5-azacitidine or decitabine  $\pm$  other therapies  $\pm$  bone marrow transplant OR with *de novo* MDS but have refused to receive hypomethylating therapy:
    - 1) INT-2 or high IPSS score OR high or very high IPSS-R *or*
    - 2) Secondary MDS (defined as MDS developing in a patient with an antecedent hematologic disorder or any patient with prior chemotherapy or radiation exposure) *or*
    - 3) INT-1 IPSS or intermediate R-IPSS MDS with excess blasts ( $\geq 5\%$  blasts in BM) or transfusion-dependency *or*
    - 4) MDS progressing to oligoblastic AML with 21-30% BM blasts *or*
    - 5) CMML or MDS/MPN with  $\geq 5\%$  marrow blasts, transfusion-dependency, abnormal karyotype, or proliferative features (white blood cell count  $\geq 13,000/\mu\text{L}$ , splenomegaly on physical examination, or extramedullary disease)
5. ECOG performance status of  $\leq 2$  at study entry or Karnofsky  $\geq 60\%$  (**Appendix C**).
6. Laboratory test results within these ranges:
  - ❖ Creatinine level of 3 mg/dL or lower
  - ❖ Total bilirubin  $\leq 3$  mg/dL unless due to Gilbert's syndrome, hemolysis, or ineffective hematopoiesis
  - ❖ AST (SGOT) and ALT (SGPT)  $\leq 3$  x ULN
  - ❖ WBC  $\leq 10,000/\mu\text{L}$
7. Patients must not have received any other treatment for their disease, including hematopoietic growth factors, aside from hydroxyurea for count control, within three weeks of beginning the trial, and should have recovered from all toxicities of prior therapy (to grade 0 or 1).

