### **7.3. Measurement of Response / Response Criteria:**

The primary endpoint of clinical response is defined by the International Working Group recommendations (see Appendix A1-A3) for therapeutic trials in AML and MDS and includes CR, complete remission with incomplete count recovery (CRi, formerly known as morphologic leukemia-free state or marrow CR), partial remission (PR), HI, SD, and PD (Cheson et al., 2003). We will also include an assessment of HI per MDS IWG-2006 recommendations as one of our secondary endpoints in our AML patients (see Appendix A2). In addition to the criteria in Appendix A1, the following will be considered as PD:

- 1) A significant increase in bone marrow blasts beyond 4 weeks of starting the drug:
  - a. if baseline 51-100% blasts – an increase of greater than 50% of baseline
  - b. if baseline 26-50% blasts – an increase up to 2 x the baseline
  - c. if baseline 0-25% blasts – an increase up to 3 x the baseline
- 2) A rising peripheral WBC after adequate dosing with hydroxyurea (see section 5.3 above)

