## 11. STATISTICAL CONSIDERATIONS

### 11.1. Study design & endpoints:

In the dose-escalation part of the study, there will be 3 dose levels (dose level 1 [DL1] with 50 mg, DL2 with 75 mg, and DL3 with 100 mg), with 1 additional dose level to be only used if excessive toxicity noted at the DL1. There will be no intra-patient dose escalation. Dose-escalation rules are defined through a standard 3+3 algorithm as outlined in Section 5.2.

The phase II expansion part of the study will aim to recruit a total of 27 patients with either R/R-AML or HR-MDS, and there will be an interim analysis after 13 patients for futility through a Simon two-stage minimax design based upon a Type I error rate of 0.05, power of 0.8, response probability of poor drug 0.05, and response probability of good drug of 0.2, based on prior relapsed and refractory AML trials and CTEP data on non-pediatric oncology trials from 2001 to 2012 (Itzykson et al., 2015; Ritchie et al., 2013; Thol et al., 2015; Yoko Korenaga Fukuda, 2014). Stage 1 will enroll 13 patients at the RP2D and will require at least 1 response for

continued enrollment to Stage 2, to reach the total of 27 patients. A total of 4 or more responses out of 27 patients will be considered encouraging evidence for future larger clinical trials of IRX5183.

Response will be defined per IWG criteria as CR, CRi, or PR for AML patients and as CR, CRi, PR, or HI for MDS patients (see definitions in Appendix A) and will be determined with each BM assessment. The composite of these responses across our study population will be referred to as the overall response rate (ORR). Rates of CR, CRi, PR, HI, and the composite endpoint of ORR will be summarized and reported with an exact 95% confidence interval.

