### **11.8.2. Evaluation of response:**

All patients included in the study that complete 2 cycles of therapy will be assessed for response to treatment, even if there are major protocol treatment deviations or if they are ineligible. The primary endpoint to the dose expansion phase is response per IWG criteria after receiving at least 2 cycles of therapy. Only those patients who have measurable disease present at baseline, have received at least 2 cycles of therapy, and have had their disease re-evaluated will be considered evaluable for response. These patients will have their response classified according to the definitions stated in Appendix A. Patients who exhibit objective disease progression prior to the end of cycle 2 will be considered not evaluable and will be taken off study.

An incorrect treatment schedule or drug administration does not result in exclusion from the analysis of the response rate. Patients with disease progression, death due to their disease, and death due to toxicity prior to completion of induction therapy will be excluded from the primary analysis. This will prevent dismissal of an active drug based on progression in patients with highly refractory disease who are unable to receive enough of the drug to see a clinical benefit. Patients who are unable to complete induction therapy for any reason will be treated as missing data and additional patients will be recruited in their place to reach our target sample size of 27 for phase II.

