**APPENDIX A2. Modified International Working Group (IWG)-2006 response criteria for altering natural history of MDS.**

Category	Response criteria (responses must last at least 4 wk)
Complete remission	
Bone marrow: <math>\leq 5\%</math> myeloblasts with normal maturation of all cell lines*
 
Persistent dysplasia will be noted**†
 
Peripheral blood‡
 
Hgb <math>\geq 11</math> g/dL
 
Platelets <math>\geq 100 \times 10^9/L</math>
 
Neutrophils <math>\geq 1.0 \times 10^9/L</math>†
 
Blasts 0%

Partial Remission	
All CR criteria if abnormal before treatment except:
 
Bone marrow blasts decreased by <math>\geq 50\%</math> over pretreatment but still <math>> 5\%</math>
 
Cellularity and morphology not relevant

Marrow CR†	
Bone marrow: <math>\leq 5\%</math> myeloblasts and decrease by <math>\geq 50\%</math> over pretreatment†
 
Peripheral blood: if HI responses, they will be noted in addition to marrow CR†

Stable disease	Failure to achieve at least PR, but no evidence of progression for $> 8$ wks
Failure	Death during treatment or disease progression characterized by worsening of cytopenias, increase in percentage of bone marrow blasts, or progression to a more advanced MDS FAB subtype than pretreatment
Relapse after CR or PR	
At least 1 of the following:
 
Return to pretreatment bone marrow blast percentage
 
Decrement of <math>\geq 50\%</math> from maximum remission/response levels in <math>\square</math>granulocytes or platelets
 
Reduction in Hgb concentration by <math>\geq 1.5</math> g/dL or transfusion dependence

Cytogenetic response	
Complete
 
Disappearance of the chromosomal abnormality without appearance of new ones
 
Partial
 
At least 50% reduction of the chromosomal abnormality
 
For patients with:

Disease progression	
Less than 5% blasts: <math>\geq 50\%</math> increase in blasts to <math>> 5\%</math> blasts
 
5%-10% blasts: <math>\geq 50\%</math> increase to <math>> 10\%</math> blasts
 
10%-20% blasts: <math>\geq 50\%</math> increase to <math>> 20\%</math> blasts
 
20%-30% blasts: <math>\geq 50\%</math> increase to <math>> 30\%</math> blasts
 
Any of the following:
 
At least 50% decrement from maximum remission/response in granulocytes or platelets
 
Reduction in Hgb by <math>\geq 2</math> g/dL
 
Transfusion dependency <math>\square</math>

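### MDS and CMML patients can enter with marrow blasts of 5% or less, and a halving of that low count then scores as a primary response because marrow CR has no minimum baseline

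*Combined protocol and SAP*

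**What the plan says.** **Entry.** Under item 4B of section 3.1, only route (4), with 21-30% blasts, guarantees blasts above 5%. Route (1) uses the IPSS or IPSS-R category. Route (2) is "Secondary MDS (defined as MDS developing in a patient with an antecedent hematologic disorder or any patient with prior chemotherapy or radiation exposure", at any blast level. In routes (3) and (5) a blast level of 5% or more is one alternative beside others such as transfusion dependency or, in (5), an abnormal karyotype.

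**Response.** Section 11.1 counts CR, CRi, PR or HI for MDS, and section 7.2 item 13 uses the same list for time to first response. Section 7.3 glosses the term as "CRi, formerly known as morphologic leukemia-free state or marrow CR". Appendix A2 asks of marrow CR only that blasts be at or below 5% and have fallen by at least half. No improvement in counts is needed: "Peripheral blood: if HI responses, they will be noted in addition to marrow CR". Responses under A2 must last at least 4 weeks.

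**Stage 1 list.** The synopsis and section 5.1 give CR, PR or HI for MDS, without CRi.

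**Evaluability.** Section 11.8.2: "Only those patients who have measurable disease present at baseline, have received at least 2 cycles of therapy" and been re-evaluated are evaluable. Measurable disease is not defined for MDS. The same section opens by saying that everyone who completes two cycles is assessed for response.

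**Decision rule.** "Stage 1 will enroll 13 patients at the RP2D and will require at least 1 response for" continuation, and "A total of 4 or more responses out of 27 patients will be considered encouraging evidence".

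**The concern.** Marrow CR is meant to record clearance of excess blasts. In a patient who had no excess, it records a change between two small numbers, and a differential count can produce that change with no effect of the drug.

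The plan guards its other MDS responses better. PR needs blasts still above 5% after the fall, so it cannot be reached from 5% or less. Each HI line in Appendix A3 requires a pretreatment cytopenia. Marrow CR has no comparable baseline condition.

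The entry wording adds to this. It defines refractory as failure to achieve CR, PR or HI. A patient whose best result on a hypomethylating agent was marrow CR alone can therefore enter as refractory with blasts of 5% or less, although the same category counts as success here.

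The trial's conclusion turns on four responders in 27, so one or two spurious scores matter.

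**Working it through.** **1. The plan's design.** Section 11.1 gives "Type I error rate of 0.05, power of 0.8, response probability of poor drug 0.05" and "response probability of good drug of 0.2". The probability of a positive trial at response rate p is

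P(p) = sum over x = 1 to 13 of Bin(x; 13, p) × Pr[Bin(14, p) ≥ 4 − x].

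This gives P(0.05) = 0.0416 and P(0.20) = 0.801. The chance of stopping at stage 1 under the null is 0.95^13 = 0.513. A full minimax search also returns 13/27 with these cut-offs, so the design is reproduced. It has little slack: P(p) passes 0.05 once p exceeds about 0.0531.

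**2. Low blasts at entry, from Appendix B.**
- IPSS: blasts below 5% (0) + poor karyotype (1.0) + 2/3 cytopenias (0.5) = 1.5, which is INT-2.
- IPSS-R: blasts above 2% and below 5% (1) + very poor cytogenetics (4) = 5, which is high risk.

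So route (1) admits such patients, and routes (2), (3) and (5) do so on their wording.

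**3. How often noise halves the count (assumptions).** Suppose the true blast fraction t never changes and each marrow is an independent binomial count of N cells. The documents do not give N; I use 200 and 500. To respect the 4-week rule, both the cycle 1 and cycle 2 marrows must be at or below half of baseline:

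s = sum over x = 1 to 0.05N of Bin(x; N, t) × Pr[Bin(N, t) ≤ x/2]².

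| True blasts | N = 200 | N = 500 |
|---|---|---|
| 1% | 15% | 6% |
| 2% | 7% | 1.5% |
| 3% | 3% | 0.4% |

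**4. Effect on the 4-of-27 decision.** Let f be the share of the 27 with low-blast MDS/CMML (not given in the documents) and s the false-score rate. The null rate becomes p = 0.05 + 0.95·f·s. At f = 20%:
- s = 1%: p = 0.0519, type I error 4.7%
- s = 4%: p = 0.0576, type I error 6.4%
- s = 10%: p = 0.0690, type I error 10.7%

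For the same s values the range is 4.4%, 5.2% and 7.0% at f = 10%, and 4.9%, 7.7% and 15.1% at f = 30%. At f = 20% the nominal 5% is passed at s = 0.0031/0.19, about 1.6%.

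**5. If stage 1 follows the synopsis and section 5.1.** Require at least one genuine response (rate 0.05) among the first 13, but count every score in the final 27. That is, sum the trinomial probabilities for stage 1 (genuine 0.05, false p − 0.05, none 1 − p) over at least one genuine response, each times the chance of reaching four in total. At f = 20% this gives 4.6%, 6.1% and 9.6% for s = 1%, 4% and 10%. The shorter stage 1 list barely protects the final decision.

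**The case against.** **The response lists conflict.** Under the synopsis and section 5.1, a 2%-to-1% patient is not a stage 1 responder. Appendix A2 has no category called CRi, and the sentence in 7.3 cites the AML criteria. A reader might infer that one noisy marrow certainly opens stage 2; the documents do not support that. But 11.1 defines ORR beside the 4-of-27 rule and includes CRi for MDS, and 7.3 names marrow CR, which appears as a category only in the MDS table. The final decision stays exposed.

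**Measurable disease could block it.** It could, if it were defined. As written, 11.8.2 both assesses everyone who completes two cycles and restricts evaluability, so it does not clearly exclude these patients. If it does exclude them, they are treated and then cannot count.

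**The size is assumed.** This stands. Single-marrow figures (32%, 22% and 13% at 200 cells for true blasts of 1%, 2% and 3%, from step 3 without the square) would overstate the problem, because they ignore the 4-week rule. Accepting any consecutive pair among the cycle 1, 2, 4 and 6 marrows gives 29%, 16% and 7% (200 cells) by simulation, but only the first pair exists when induction ends, which section 5.1 makes the primary assessment.

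**Patients already in CR at entry.** A reader might also infer that normal counts at entry score as CR. That route is nearly closed. Appendix A2 asks for normal maturation of all cell lines, although it also says that persistent dysplasia is noted. Section 3.1 requires relapsed or refractory disease, or de novo MDS with hypomethylating therapy refused. HI requires an abnormal pretreatment count, and PR requires blasts above 5%.

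**Conclusion.** The point holds for marrow CR/CRi. Following 3.1, 7.3, 11.1 and Appendix A2 as written, a sustained fall from one low blast count to half of it is a primary response and can count toward the four needed. Whether it can also open stage 2 cannot be settled until the response lists agree.

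The inflation is modest to material, depending on three unknowns: the share of low-blast patients, the number of cells counted, and the true blast level. With 500 cells and true blasts of 2-3%, type I error at a 20% share stays below 5%. With 200 cells and true blasts of 1-2%, the false-score rate is 7-15%, a range that contains the 10% case with type I error of 10.7%. Section 11.6 plans no stratification, so nothing fixes the MDS share. The repair is worth making because it is cheap, not because the inflation is proven.

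**What to change.** 1. In 7.3 and 11.1, state that for MDS, CMML and MDS/MPN, marrow CR/CRi counts toward ORR only if baseline marrow blasts were above 5%, and that patients entering at 5% or less are assessed mainly by HI.
2. Use one MDS response list in the synopsis, 5.1 and 11.1.
3. In 11.8.2, define measurable disease for these patients as baseline marrow blasts above 5%, or at least one Appendix A3 pretreatment cytopenia (Hgb < 11 g/dL, platelets < 100 × 10^9/L, or neutrophils < 1.0 × 10^9/L). Reconcile this with that section's opening sentence.
4. Report ORR with and without marrow CR alone.

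The cost is wording only, since baseline marrow and counts are already collected. The observed ORR may be slightly lower. Eligibility need not change.

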### 3.2. **Exclusion criteria:**

1. Any serious medical condition or uncontrolled intercurrent illness including, but not limited to, ongoing or active infection, symptomatic congestive heart failure, unstable angina pectoris, cardiac arrhythmia, laboratory abnormality, or psychiatric illness/social situations that would limit compliance with study requirements or prevent the subject from signing the informed consent form.
2. Any condition, including the presence of laboratory abnormalities, which places the subject at unacceptable risk if he/she were to participate in the study or confounds the ability to interpret data from the study.
3. Use of any other experimental drug or therapy within 21 days of baseline.
4. Known hypersensitivity or history of allergic reactions attributed to compounds of similar chemical or biologic composition to IRX5183.
5. Prior use of other retinoid therapies in the 3 months prior to enrollment in the study.
6. Patients with other active cancers receiving anti-cancer agents, with exceptions being hormonal therapy for breast or prostate cancer and skin cancers treated with local therapies only.
7. Patients who have had chemotherapy or radiotherapy within 4 weeks (6 weeks for nitrosoureas or mitomycin C) prior to entering the study or those who have not recovered from adverse events due to agents administered more than 4 weeks earlier (e.g. alopecia, hypothyroid, neuropathy, etc.).
8. Pregnant women are excluded from this study because of potential for teratogenic or abortifacient effects. Because there is an unknown but potential risk for adverse events in nursing infants secondary to treatment of the mother with IRX5183, breastfeeding should be discontinued if the mother is treated with IRX5183.

### 3.3. **Pregnancy:**

The effects of IRX5183 on the developing human fetus are unknown. For this reason, women of childbearing potential and men must agree to use adequate contraception (hormonal or barrier method of birth control; abstinence) prior to study entry and for the duration of study participation. Should a woman become pregnant or suspect she is pregnant while she or her partner is participating in this study, she should inform her treating physician immediately. Men treated or enrolled on this protocol must also agree to use adequate contraception prior to the study, for the duration of study participation, and 4 months after completion of IRX5183 administration.

Sexually active women of childbearing potential (WOCBP) must use an effective method of birth control during the course of the study, in a manner such that risk of failure is minimized. Before enrolling WOCBP in this clinical study, the investigator must review the guideline about study participation for WOCBP, which can be found in the GCP Manual for Investigators. The topics include the following:

- ❖ General Information
- ❖ Informed Consent Form
- ❖ Pregnancy Prevention Information Sheet
- ❖ Drug Interactions with Hormonal Contraceptives
- ❖ Contraceptives in Current Use
- ❖ Guidelines for the Follow-up of a Reported Pregnancy

Before study enrollment, WOCBP must be advised of the importance of avoiding pregnancy during study participation and the potential risk factors for an unintentional pregnancy. The subject must sign an informed consent form documenting this discussion. **All WOCBP MUST have a negative pregnancy test within 72 hours before receiving their first dose of IRX5183.** The minimum sensitivity of the pregnancy test must be 25 IU/L or equivalent units of HCG. If the pregnancy test is positive, the subject must not receive IRX5183 and must not be enrolled in the study. **In addition, all WOCBP should be instructed to contact the investigator immediately if they suspect they might be pregnant (e.g., missed or late menstrual period) at any time during study participation.**

If, following initiation of the investigational product, it is subsequently discovered that a study subject is pregnant or may have been pregnant at the time of investigational product exposure, including during at least 6 half-lives after product administration, the investigational product will be permanently discontinued in an appropriate manner (*e.g.*, dose tapering if necessary for subject safety). The investigator must immediately notify Io Therapeutics of this event and record the pregnancy on the Pregnancy Surveillance Form (not an SAE form). Initial information on a pregnancy must be reported immediately to Io Therapeutics, and the outcome information provided once the outcome is known. Completed Pregnancy Surveillance Forms must be forwarded to Io Therapeutics according to SAE reporting procedures. Any pregnancy that occurs in a female partner of a male study participant should be reported to the sponsor. Information on this pregnancy will be collected on the Pregnancy Surveillance Form. Protocol-required procedures for study discontinuation and follow-up must be performed on the subject unless contraindicated by pregnancy (*e.g.*, X-ray studies). Other appropriate pregnancy follow-up procedures should be considered if indicated. In addition, the investigator must report and follow-up on information regarding the course of the pregnancy, including perinatal and neonatal outcome. Infants should be followed for a minimum of 8 weeks.

#### 3.4. **Inclusion of women and minorities:**

Both men and women of all races and ethnic groups are eligible for this trial.

#### 3.5. **Off-Study Criteria:**

Patients may be removed from study for any of the following:

- Toxicity that the patient determines to be unacceptable.
- Physician determination that the continued participation in the study is no longer in the best interest of the subject
- 
- Patient elective withdraw of their consent.
- Progression of disease per criteria Appendix A and section 7.3 below.

#### 3.6. **Informed Consent:**

All patients eligible for the study must be evaluated by one of the study investigators. Informed consent must be obtained and the consent form signed. A Johns Hopkins on study form will be completed following fulfillment of the on-study requirements for laboratory work and eligibility criteria.

#### 4. PRETREATMENT PLAN

A complete history and physical examination and list of medications will be documented on each patient within two weeks of starting therapy. A **bone marrow aspirate and biopsy** confirming the suspected diagnosis will be documented within 2 weeks of enrollment.

**Clinical Laboratory Studies** within two weeks of starting therapy will include:

1. Hematologic studies: complete blood count with platelets and differential
2. Renal and electrolyte: chemistry panel (including electrolytes, creatinine, uric acid, albumin, total protein, calcium and phosphate)
3. Hepatic: serum SGOT, SGPT, alkaline phosphatase, total bilirubin
4. Coagulation: fibrinogen, PT/INR, PTT, D-dimer
5. Lipid Panel (fasting): Triglycerides, Cholesterol, LDL, HDL. Retinoids have been shown to increase triglycerides and cholesterol levels; thus, baseline levels will be checked per standard of care.

In addition to baseline laboratory tests and BM aspirate and biopsy, **quality of life assessment** will be performed per the FACTleu questionnaire (available at <http://www.facit.org/FACITOrg/Questionnaires>), administered with the help of the research team.

